6.2 Preparation/Handling/Storage/Accountability

6.2.1 Acquisition and Accountability

For detailed instructions regarding study drug acquisition and accountability, refer to the IP Instructions for Handling.

The PI is responsible for ensuring accountability of all study medication supplied and appropriate storage and allocation of these supplies.

The PI is responsible for ensuring that all study medication received at the site are inventoried and accountability performed, and that dispensed study medication is recorded in both the eCRF and the Study Medication Accountability Logs. The PI, or designee, will verify study medication accountability with the CRA during site visits. Any discrepancies should be investigated. The PI will not supply study medication or rescue medication to any person except those named as Sub-Is on Form FDA 1572, designated staff, and study participants in this study and will not dispense study medication or rescue medication from any sites other than those listed on Form FDA 1572. Study medication and rescue medication may not be relabeled or reassigned for use by other study participants.

All unused or damaged study medication and/or rescue medication will be returned, and unit counts will be performed whenever medication is returned. The site must account for all study medication received. The site will retain and store all study medication and rescue medication until inventoried by the monitor.

All unused or damaged (e.g., films that were torn during opening of the foil package) study medication and/or rescue medication will be returned to the CRO's return vendor along with copies of the Study Medication Accountability Logs.

6.2.2 Formulation, Appearance, Packaging, and Labeling

Phenobarbital Sodium Injection, USP is a sterile solution for intramuscular or slow intravenous administration as a long-acting barbiturate. Each mL contains phenobarbital sodium either 55 mg or 90 mg, alcohol 140 mg/mL, propylene glycol ~779mg/mL or 754mg/mL, respectively, and no benzyl alcohol in water for Injection; hydrochloric acid and sodium hydroxide added, if needed, for pH adjustment. Chemically, phenobarbital sodium is 2,4,6(1H,3H,5H)-Pyrimidinetrione,5-ethyl-5-phenyl-, monosodium salt.

The packaging and labeling will be detailed in the IP Supply Plan.

6.2.3 Product Storage and Stability

Phenobarbital vials can be stored at 15°-25°C (68°-77°F), excursions permitted between 15°-30°C (59°-86°F) are allowed provided that the mean kinetic temperature (MKT) does not exceed 25C. Transient spikes up to 40C are allowed only if they do not exceed 24 hours.

Do not use if solution is discolored or contains a precipitate.

Detailed storage conditions of phenobarbital prepared in syringes is described in the study provided pharmacy manual.

6.2.4 Preparation

All phenobarbital treatment doses will be prepared by the unblinded investigational pharmacist. The investigational pharmacist will be unblinded (have access to the randomization code) and will not be involved in the assessment or medical management of the neonate. All other study personnel will be blinded to the phenobarbital dose treatment administered. Each study treatment arm will be prepared in the same total volume of administration in order to maintain the study blind.

Further details are provided in the IP Instructions for Handling (also known as Pharmacy Manual).

6.3 Measures to Minimize Bias: Randomization and Blinding

Study participants will be assigned unique study participant numbers upon completion of the Screening Period and upon achieving the seizure criteria.

A unique randomization number will be assigned by an interactive web response system (IWRS) once eligibility for the Treatment Period of the study has been determined. Randomization codes will be prepared by an external-to-study, unblinded biostatistician.

Detailed instructions for contacting the IWRS will be provided in the Study Manual. The PI or designee will use the IWRS to determine which investigational medicinal product (IMP) will be

dispensed to a given study participant for the Treatment Period of the study. The unblinded investigational pharmacist will prepare the IMP (both first and second loading dose for each treatment arm [labeled A and B in IWRS for unblinded pharmacist]) after the informed consent is signed and provide to the PI or designee for storage in the NICU's pyxis machine, if possible. At time of randomization, the PI or designee will contact the IWRS for the randomization code and syringe code prior to first dose administration. The IWRS will be contacted again if second loading dose administration is needed.

6.3.1 Unblinding

The Investigator may unblind an individual study participant's treatment in an emergency when knowledge of such treatment may have an impact on further treatment decisions or aid in the emergency treatment of the study participant. Every effort must be made to contact the Medical Monitor prior to any unblinding of the study drug. The circumstances that lead to unblinding will be promptly communicated via telephone and in writing to the Medical Monitor.

6.4 Study Drug Compliance

The PI, or designee, will verify study medication accountability with study participants during site visits.

6.5 Concomitant Therapy

6.5.1 Allowed Concomitant Medication

For this protocol, a prescription medication is defined as a medication that can be prescribed only by a properly authorized/licensed clinician. Medications to be reported in the Case Report Form (CRF) are concomitant prescription medications, over-the-counter medications (if applicable) and supplements (if applicable).

Only the short acting benzodiazepine lorazepam and midazolam administered ≥ 8 hours before enrollment will be permitted prior to study entry.

6.5.2 Second-line Anticonvulsants

Non-phenobarbital second line anticonvulsants/antiseizure medications are allowed and include:

- Fosphenytoin
- Levetiracetam
- Topiramate
- Clonazepam
- Lidocaine

7 Study Drug Discontinuation and Participant Discontinuation/Withdrawal

7.1 Discontinuation of Study Drug

Discontinuation from intravenous phenobarbital does not mean discontinuation from the study, and remaining study procedures should be completed as indicated by the study protocol. If a clinically significant finding is identified (including, but not limited to changes from baseline) after enrollment, the investigator or qualified designee will determine if any change in participant management is needed.

The data to be collected at the time of study drug discontinuation will include the following:

- Vital Signs
- Collection and review of Laboratory Tests (Hematology, Chemistry and Coagulation)
- cvEEG Assessment
- Clinical Seizure Assessment
- Phenobarbital PK Samples
- Recording of Additional Anticonvulsant Medication
- Concomitant Medication Review
- Adverse Events Evaluation

7.2 Participant Discontinuation/Withdrawal from the Study

Parents/Legal Guardians are free to withdraw their study participants in the study at any time upon request.

An investigator may discontinue or withdraw a study participant from the study for the following reasons:

- If any clinical adverse event (AE), laboratory abnormality, or other medical condition or situation occurs such that continued participation in the study would not be in the best interest of the study participant
- If the participant meets an exclusion criterion (either newly developed or not previously recognized) that precludes further study participation
- Participant unable to receive study drug

The reason for study participant discontinuation or withdrawal from the study will be recorded on the Study Participant Disposition Case Report Form (CRF). Study participants who sign the informed consent form and are randomized but do not receive the study drug may be replaced. Study participants whose parent/legal guardian sign the informed consent form, and are randomized and receive the study drug, and subsequently withdraw, or are withdrawn or discontinued from the study, will not be replaced.

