3.2 Endpoints

3.2.1 Primary Endpoint

Percent of neonates who do not require additional seizure treatment after the first dose of phenobarbital during the first 24 hours after treatment.

Time zero (T0) will be defined as the start of the first loading dose 30-minute infusion.

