5.2 Exclusion Criteria

An individual who meets any of the following criteria will be excluded from participation in this study:

1. Received anticonvulsant treatment, including phenobarbital, prior to randomization (with exception of lorazepam and midazolam administered ≥ 8 hours before enrollment)
2. Strong suspicion or confirmed diagnosis of brain malformation, inborn error of metabolism genetic syndrome, or major congenital malformation prior to randomization

3. Seizures responding to correction of hypoglycemia, hypocalcemia or any other metabolic disorder
4. Death appears to be imminent as assessed by the NICU attending physician
5. Is currently enrolled in another study assessing the same and/or similar primary/secondary endpoints with/without drug treatment.

Study participants who may be already participating in another neonatal clinical trial (e.g., registry or observational) that meet all MI-5780 inclusion criteria and none of the MI-5780 exclusion criteria as well as can meet study assessment requirements, can be enrolled into this study. In addition, study participants enrolled in this trial can enroll in other neonatal trials as long as 1) the inclusion criteria for study MI-5780 continue to be met 2) none of the exclusion criteria for study MI-5780 are met 3) the other study will not result in minor or major MI-5780 protocol deviations.

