9.4.2 Analysis of the Primary Efficacy Endpoint(s)

The primary endpoint will be summarized by number and percent of participants with events and compared by a log binomial model (a generalized linear model [GLM]) that includes treatment as a study variable, which will generate risk ratio (RR) together with their 95% CIs of having a primary outcome between high dose and low dose groups. A study participant who is withdrawn from the study within the first 24 hours after treatment will be considered not to have achieved the primary endpoint. Treatment of such dropouts with respect to other endpoints will be specified in the SAP.

In addition, covariate adjustment will be performed by GLM model with treatment as a study variable and, gender, gestational age, birth weight, apgar scores, liver function tests, seizure etiology, therapeutic hypothermia and pre-treatment seizure burden as covariates. From this

model, adjusted RR together with their 95% confidence interval will be derived. Imputation for these baseline missing covariates will be carried out for adjusted analysis.

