5.5.2. Primary outcome

Randomised subjects with missing responses will be treated as treatment failures

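### Protocol 9.4.2 scores a neonate withdrawn before 24 h as a failure even when the outcome is known; SAP 5.5.2 does so only when it is missing, and 7.2 does not secure the outcome.

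*Protocol*

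**What the plan says.** The primary endpoint (Protocol 3.2.1) is: "Percent of neonates who do not require additional seizure treatment after the first dose of phenobarbital during the first 24 hours after treatment".

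Protocol 7.2 lists the reasons for which an investigator may withdraw a participant from the study. One of them is: "If the participant meets an exclusion criterion (either newly developed or not previously recognized) that precludes further study participation". The section covers neonates who have been randomised and dosed. It says that those who receive study drug "and subsequently withdraw, or are withdrawn or discontinued from the study, will not be replaced". It does not ask for the 24-h outcome to be collected after withdrawal.

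Protocol 7.1 treats stopping the drug differently: "Discontinuation from intravenous phenobarbital does not mean discontinuation from the study, and remaining study procedures should be completed".

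Protocol 9.4.2 gives the scoring rule for the primary endpoint: "A study participant who is withdrawn from the study within the first 24 hours after treatment will be considered not to have achieved the primary" (quotation cut before its last word). It makes no exception for the reason or for an outcome already known. It leaves to the SAP only the handling of dropouts for other endpoints.

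SAP 5.5.2 gives a different trigger: "Randomised subjects with missing responses will be treated as treatment failures". It neither repeats nor withdraws the protocol rule. SAP 4.1 keeps all randomised subjects with valid consent in the ITT set. SAP 4.2 removes those who did not qualify for randomisation from the per-protocol set, which is supportive only.

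**The concern.** Some exclusion criteria in Protocol 5.2 can come to light after dosing. Study drug is to start at most two hours after qualifying seizures are recognised (Protocol 4.1). Anticonvulsants given before randomisation may be discovered late. Criterion 3, "Seizures responding to correction of hypoglycemia, hypocalcemia or any other metabolic disorder", may be recognisable only once correction has had time to act. Criterion 4, imminent death, can develop later.

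Suppose a dosed neonate needs no further seizure treatment and is then withdrawn at 15 h because one of these criteria is recognised. The neonate is still a NICU inpatient, so whether further treatment was given by 24 h can normally be read from the record. Under Protocol 9.4.2 the result is nevertheless a failure. Under SAP 5.5.2 it is a success if the response was recorded and a failure if it was not, and 7.2 does not ensure that it is recorded.

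Three things are at stake:

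- The same neonate can be scored two ways, depending on which document the programmer follows.
- True successes become failures, which lowers both rates and costs power.
- If withdrawal differs between arms, the comparison is biased.

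Seizure burden at 24 and 48 h is affected too, because SAP 5.5.3 imputes nothing for secondary outcomes.

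**Working it through.** **1. The plan's own figure.** Inputs from Protocol 9.2 and SAP 3.6: 70% (high dose) and 50% (low dose), alpha 0.05, power 80%. The alternative in Protocol 9.1 is two-sided, and allocation is 1:1 (Protocol 4.1). With pooled variance under the null and mean rate 0.60:

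n per arm = [1.960 × √(2 × 0.60 × 0.40) + 0.842 × √(0.50 × 0.50 + 0.70 × 0.30)]² / 0.20² = 93.

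Then 186 / 0.95 = 195.8, so 196 are randomised, 98 per arm. Both stated figures reproduce.

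**2. Effect of failure scoring.** Let w be the share of each arm withdrawn before 24 h on this ground, unrelated to response. The documents give no value, so w is an assumption. Each success rate p becomes p(1 − w), and the difference becomes 0.20 × (1 − w). With p̄ the mean of the two rates:

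power = Φ{[difference × √98 − 1.960 × √(2p̄(1 − p̄))] / √(p₁(1 − p₁) + p₂(1 − p₂))}.

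For w = 5% the rates are 66.5% and 47.5%, and p̄ = 0.57:

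(0.19 × 9.899 − 1.960 × √0.4902) / √0.47215 = (1.881 − 1.372) / 0.687 = 0.740, so power is 77.0%.

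| w in each arm | High / low success | Difference (points) | Power, 98 per arm | n per arm for 80% |
|---|---|---|---|---|
| 0% | 70.0 / 50.0 | 20.0 | 82.0% | 93 |
| 1% | 69.3 / 49.5 | 19.8 | 81.1% | 96 |
| 2% | 68.6 / 49.0 | 19.6 | 80.1% | 98 |
| 3% | 67.9 / 48.5 | 19.4 | 79.1% | 101 |
| 5% | 66.5 / 47.5 | 19.0 | 77.0% | 106 |
| 10% | 63.0 / 45.0 | 18.0 | 71.8% | 120 |

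The risk ratio stays at 1.40 in every row, because both rates are multiplied by the same factor.

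**3. Why the 5% allowance does not cover this.** The allowance assumes that lost neonates leave the denominator: 98 × 0.95 ≈ 93 per arm, which gives 80.0%. Failure scoring keeps them in the denominator as failures, and at 5% power is 77.0%.

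**4. If every withdrawn neonate would have been a success.** Taking 5 points off each arm gives 65% vs 45%. The difference stays at 20 points and power is 80.8%. The shrinkage in step 2 therefore depends on withdrawal being unrelated to response.

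**5. Unequal withdrawal.** With 98 per arm:

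- 5% in the high-dose arm only: 66.5% vs 50%, difference 16.5 points, power 65.1%.
- 5% in the low-dose arm only: 70% vs 47.5%, difference 22.5 points, power about 90%.
- No true effect (50% in both arms) with 5% withdrawn from the high-dose arm only: spurious difference of −2.5 points, two-sided rejection rate 6.4%.
- The same with 10%: −5 points and 10.8%, against a nominal 5%.

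**The case against.** The strongest reply is that the route is narrow.

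- Withdrawal under 7.2 is permitted, not required, and only where the criterion precludes further participation. A reader might infer that every neonate found to meet an exclusion must leave and be failed. No passage says so.
- A reader might also count any metabolic or genetic diagnosis made after dosing as a trigger. Criterion 2 reads: "Strong suspicion or confirmed diagnosis of brain malformation, inborn error of metabolism genetic syndrome, or major congenital malformation prior to randomization". If neither suspicion nor diagnosis existed before randomisation, that criterion is not met. Criterion 1 is tied to the same time point, so it can be recognised late but cannot newly develop.
- Only would-be successes change status. A neonate already given further seizure treatment is a failure under either rule.
- Protocol 9.4.1 sends analysis detail to the SAP, and under SAP 5.5.2 alone a recorded response stands.
- The trial is blinded, and the documents give no reason to expect more withdrawals on this ground in one arm.
- A reader might infer that safety follow-up is lost. Protocol 4.1 and the schedule in 1.3 require assessments at early discontinuation. Protocol 8.3.4 records adverse events to 7 days and serious ones to 30 days after participation ends. What is lost is scheduled measurement after withdrawal.

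All of this stands and limits the size. It does not settle the conflict, because 9.4.2 defers to the SAP only for other endpoints. Nor does the SAP rule protect an outcome that 7.2 does not require anyone to collect.

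**Conclusion.** The point holds in a limited form. Protocol 9.4.2 and SAP 5.5.2 give different results for a neonate withdrawn before 24 h with a known success, and 7.2 does not ensure that the outcome is known. The ITT analysis can therefore record a true success as a failure.

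The size depends on an assumed w. At up to about 2% in each arm the trial keeps its planned 80% power. At 5% it loses about 5 points of power against full observation, and 1 point of risk difference. These figures assume withdrawal equal between arms and unrelated to response. Unequal withdrawal would bias the estimate in either direction, but the documents do not show that it should be expected.

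A reader might infer that the sample size is wrong or that this ground for withdrawal should be deleted. Neither follows. The sample size reproduces. Deleting the ground would reach into participant protection, and would leave the other exits in 7.2 and 4.1 untouched. The defect lies in how the outcome is collected and scored after withdrawal.

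**What to change.** 1. Leave the investigator's withdrawal grounds as they are. Add to Protocol 7.2 that, unless consent is withdrawn, use of additional seizure treatment up to 24 h after the start of the first dose is still recorded. Where monitoring continues, existing cvEEG seizure data up to 48 h should be recorded too.
2. Reconcile Protocol 9.4.2 with SAP 5.5.2 before unblinding. In the ITT analysis, use the observed 24-h outcome whenever it is known, and impute failure only when it is truly unobserved.
3. Keep the per-protocol analysis in SAP 4.2 as the sensitivity analysis for neonates ineligible at randomisation. It does not address criteria that develop later; items 1 and 2 do.

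The cost is a sentence or two in each of the three sections and a little extra data collection on inpatients. A few ineligible neonates will contribute their real outcomes, as ITT intends. No dose or treatment rule changes.

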7.3 Lost to Follow-up

Not applicable

7.4 Study Stopping Rules

The trial DSMB will decide on terminating the trial based on stopping rules defined under [Section 7.4.2](#). Stopping rules will be reviewed along with information regarding conduct and progress of the study, study participant accrual, protocol compliance and other study issues. After each meeting, a recommendation to continue or terminate the study will be provided. DSMB responsibilities, board process, communications and meeting format details are defined in the DSMB Charter.

The study may be prematurely terminated at any time by the Sponsor, IRB and or Investigator in the interest of the study participant safety and welfare. The Sponsor reserves the right to discontinue the trial at any time for any reason.

7.4.1 Stopping rules for study participants

7.4.1.1 *Efficacy*

Study participants will not be stopped in the trial if seizure cessation is not achieved with one or two doses of phenobarbital. Study participants will be placed on second-line treatments per institutional protocol/standard operating procedures and will continue to be observed. Sponsor is not providing sites with second-line anticonvulsant treatments.

7.4.1.2 *Safety*

Newborns who will be enrolled in this study are at high risk for several serious medical complications and death related to underlying etiology of their seizures. It is very unlikely that phenobarbital will result in death or any serious adverse event. The following adverse events not described in the investigator brochure for phenobarbital will be considered expected adverse events in this population:

- Clinical or electrographic seizures
- Multiorgan Failure
- Abnormal lab values associated with organ failure
- Death
- Any other adverse events associated with systemic asphyxia and hypoxic-ischemic encephalopathy in newborns

Any adverse events that are expected, not related to phenobarbital, and not severe in nature will be recorded in the database and reviewed at regular meetings of the DSMB. The DSMB will be able to review significant trends of adverse events at their meetings, since the DSMB will be the only party not blinded in this trial. After review of the data, the DSMB will report to NEMA regarding the risks of the study and whether the risks are consistent with what is described in the informed consent form. These reports will be provided by NEMA to the local IRBs for determining continuing review, and to the FDA for annual IND safety reports.

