7.4.2 Stopping rules for Overall Trial

The DSMB may recommend stopping the study for the following reasons:

- The data show a clinically important risk of serious adverse effects in one or both of the treatment arms.
- It becomes clear that successful completion of the study is not feasible (e.g. there is an excess of study participant dropout, missing data, lack of recruitment etc).

7.4.2.1 *Safety-Continuous Monitoring*

Adverse Events will be continuously monitored by the investigator, clinical research associate, CRO Medical Monitor and Sponsor.

If while continuous monitoring the investigator deems an adverse event to be severe, unexpected and possibly related to phenobarbital, the investigator will report the event to NEMA within 24 hours of the event. These unanticipated adverse events will events will also be reported by the PI to the local IRB in accordance with the local IRB policies. NEMA will be responsible for reporting the unanticipated adverse events to all DSMB members within 24 hours of receiving the report, and to the FDA in an IND safety report in accordance with FDA regulations. The DSMB will determine if the adverse event changes the known risk to study participants. If the information changes the known risk to study participants, the DSMB's report regarding the change in risk will be released to all participating investigators by NEMA. The DSMB may request changes to the DSMB Charter and or potentially halt the trial.

7.4.2.2 *Safety-Interim Monitoring*

The DSMB will evaluate the study after the first 10% and 50% of randomized study participants.

Criteria to be evaluated are outlined in detail in the committee charter.

8 Study Assessments and Procedures

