- **Not Related:** The AE is completely independent of study drug administration, and/or evidence exists that the event is definitely related to another etiology. There must be an alternative, definitive etiology documented by the clinician.

As a guide, some questions to ask/think about when addressing drug-related causality may include:

- Is the AE a known reaction of the drug?
- Is the AE similar to other adverse events listed the investigator's brochure or consent documents?
- Has the AE occurred before in this study?
- Is the AE reasonably temporally related to the drug?
- Does the AE improve or disappear when the drug is discontinued? What happens on re-test?
- Was the AE present at the baseline assessment of the study participant or in the study participant's recent medical history?
- Can the AE be reasonably explained by the study participant's clinical disease status?
- Are there any other potential causes for the AE?

8.3.3.2 *Expectedness*

An unexpected adverse event is one where the nature or intensity is not consistent with the information in the Investigator's Brochure (for compounds in development) or the USPI (for compounds marketed in the US).

Furthermore, reports which add significant information on specificity or so far unexpected severity of a known, already documented adverse reaction constitute unexpected events. For example, an event more specific or more severe than described in the USPI or Investigator's Brochure would be considered 'unexpected'.

Expectedness will be assessed by the CRO Medical Monitor and Sponsor.

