8.3.6 Serious Adverse Event Reporting

The study clinician will immediately report (within 24 hours) to the CRO any serious adverse event, whether or not considered study drug related, including those listed in the protocol or investigator brochure and must include an assessment of whether there is a reasonable possibility that the study drug caused the event. Study endpoints that are serious adverse events (e.g., all-cause mortality) must be reported in accordance with the protocol unless there is evidence suggesting a causal relationship between the study drug and the event (e.g., death from anaphylaxis). In that case, the investigator must immediately report the event to the CRO.

All serious adverse events (SAEs) will be followed until satisfactory resolution or until the site investigator deems the event to be chronic or the participant is stable. Other supporting documentation of the event may be requested by the Data Coordinating Center (DCC)/study Sponsor and should be provided as soon as possible.

The CRO will be responsible for notifying the Food and Drug Administration (FDA) of any unexpected fatal or life-threatening suspected adverse reaction as soon as possible, but in no case later than 7 calendar days after the CRO's initial receipt of the information. In addition, the Sponsor must notify FDA and all participating investigators in an Investigational New Drug (IND) safety report of potential serious risks, from clinical trials or any other source, as soon as possible, but in no case later than 15 calendar days after the CRO determines that the information qualifies for reporting.

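### The protocol defines an expected adverse event in two contradictory ways, so a possibly drug-related death in either arm could be kept out of the 24-hour DSMB notice

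*Protocol*

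**What the plan says.** Protocol section 7.4.1.2 (Safety) names a set of events that, by its own account, the Investigator's Brochure does not describe, and says that they "will be considered expected adverse events in this population". The list that follows is clinical or EEG seizures, multiorgan failure, laboratory changes of organ failure, death, and any other event associated with asphyxia and HIE. It applies to both arms and is not confined to events thought unrelated to study drug. The only handling that the section then gives is routine: "Any adverse events that are expected, not related to phenobarbital, and not severe in nature will be recorded in the database" and looked at in regular DSMB meetings.

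Section 7.4.2.1 sets the expedited route. It starts when "the investigator deems an adverse event to be severe, unexpected and possibly related to phenobarbital". The investigator reports to NEMA within 24 hours of the event, and "NEMA will be responsible for reporting the unanticipated adverse events to all DSMB members within 24 hours of receiving the report".

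Section 8.3.3.2 calls an event unexpected when its "nature or intensity is not consistent with the information in" the Investigator's Brochure or the US label (USPI), and gives the assessment to the CRO Medical Monitor and Sponsor.

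Section 8.3.6 sends every SAE to the CRO within 24 hours, whatever its relation to drug. It requires FDA notice within 7 days of "any unexpected fatal or life-threatening suspected adverse reaction", and an IND safety report of potential serious risks to FDA and investigators within 15 days. Sections 8.4.1 and 8.4.2 add an Unanticipated Problem route that also requires the event to be unexpected and that does reach the DSMB.

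**The concern.** A death that an investigator thinks possibly related to phenobarbital is expected under one section and unexpected under another, and nothing in the protocol says which section governs. Three reporting routes turn on that word.

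Dose-response for safety is part of the primary objective (section 3.1.1). Section 7.4.1.2 describes the DSMB as the only unblinded party. Sections 4.1 and 6.2.4 also unblind the pharmacist, who takes no part in assessing the neonate. The DSMB is thus the one safety body placed to see whether deaths fall unevenly between arms. At stake is whether it hears promptly of a single possibly related death.

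The last item on the list widens the problem. HIE is the first eligible etiology named in section 5.1, so a clause that takes in any event associated with asphyxia or HIE could make many serious events in this population expected.

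**Working it through.** The contradiction itself involves no arithmetic. Take one case, a death assessed as possibly related to phenobarbital in either arm, and follow it through each route under each definition.

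| Route | Condition | If 7.4.1.2 governs | If 8.3.3.2 governs | Names the DSMB? |
|---|---|---|---|---|
| 24-hour notice, 7.4.2.1 | severe, unexpected and possibly related | not triggered | triggered | yes |
| 7-day FDA notice, 8.3.6 | unexpected fatal or life-threatening suspected reaction | not triggered | triggered | no |
| Unanticipated Problem, 8.4.1 and 8.4.2 | unexpected in nature, severity or frequency, partly in light of the population | may not be triggered | arguable on 8.4.1's own test | yes |
| Routine DSMB meeting review, 7.4.1.2 | expected, unrelated and not severe | not met | not met | yes |
| 24-hour SAE report, 8.3.6 | any SAE | applies | applies | no |
| 15-day IND report, 8.3.6 | potential serious risk | can apply | can apply | no |

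The third column shows the gap. If 7.4.1.2 governs, the death fails the expedited route because it is expected. It fails the routine route because it is neither unrelated nor non-severe. Section 7.4 then assigns it to no route.

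The fourth column assumes that the Brochure is the reference, or that the US label is equally silent on the event. Neither is among the documents.

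The assessor differs as well. Under 7.4.2.1 the investigator decides whether the event is unexpected, with the 7.4.1.2 list in the same section. Under 8.3.3.2 the CRO Medical Monitor and Sponsor decide.

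**Timing.** The plan's sample size fixes where the DSMB looks fall, so it is checked first. Inputs (section 9.2): 70% and 50%, alpha 0.05 (taken as two-sided, as in section 9.1), power 80%.

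- n per group = [1.960 × √(2 × 0.60 × 0.40) + 0.842 × √(0.70 × 0.30 + 0.50 × 0.50)]² / 0.20² = 93, as stated.
- 186 / 0.95 = 195.8, so 196 randomized, as stated.
- Looks at 10% and 50% (section 7.4.2.2): 0.10 × 196 = 19.6, about 20; 0.50 × 196 = 98. At 1:1 allocation this is about 10 and 49 per arm.
- Expedited route: 24 h to NEMA + 24 h to the DSMB = about 48 h.
- Without it: the next scheduled review. Section 10.1.7 sets meetings at least semiannually unless the charter says otherwise, so at most about six months.

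**Can the scheduled looks stand in for single-case notice?** The documents give no mortality rate. Assume 5%, 10% or 15% in the low-dose arm, doubled in the high-dose arm. Expected deaths are n × p. Power at two-sided 0.05 is Φ{[√n × |p₂ − p₁| − 1.960 × √(2p̄(1 − p̄))] / √(p₁(1 − p₁) + p₂(1 − p₂))}, where p̄ is the mean of p₁ and p₂.

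| Assumed rates | Deaths, 10 per arm | Power | Deaths, 49 per arm | Power |
|---|---|---|---|---|
| 5% vs 10% | 0.5 vs 1.0 | 6% | 2.5 vs 4.9 | 15% |
| 10% vs 20% | 1.0 vs 2.0 | 9% | 4.9 vs 9.8 | 28% |
| 15% vs 30% | 1.5 vs 3.0 | 12% | 7.4 vs 14.7 | 43% |

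The normal approximation is rough at 10 per arm, but the message is clear: comparing death counts at the two looks is a weak substitute for prompt review of individual cases.

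**The case against.** The strongest reply is that 8.3.3.2 is the protocol's formal definition and sits in the same chapter as the 7-day FDA notice, so it is the natural reference for that notice. Under it a possibly related death absent from the Brochure is unexpected and reportable. Every SAE reaches the CRO within 24 hours, with immediate reporting where there is evidence that drug caused a death. The CRO Medical Monitor and Sponsor would therefore see the case whatever the investigator called it. The 15-day report does not use the word unexpected. The Unanticipated Problem test includes frequency, so an excess of deaths could qualify even if death as such is anticipated. Section 7.4.1.2 speaks of risks from underlying etiology and of trends, which suggests that the list was meant for aggregate review.

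Much of this stands. A reader might infer that a possibly related death would certainly miss the expedited DSMB and regulatory routes. The documents do not support that, because it takes 7.4.1.2 to govern when 8.3.3.2 gives the opposite answer. A reader might also infer that the gap concerns the higher dose. It does not: the list covers both arms and investigators are blinded.

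The reply does not settle the DSMB notice. The SAE and 15-day reports name the CRO, FDA and investigators, not the DSMB. The Unanticipated Problem route reaches the DSMB, but it weighs the population's characteristics, which is the basis of the 7.4.1.2 list. That 8.3.3.2 gives another answer is the contradiction, not its resolution.

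**Conclusion.** The point holds as an internal contradiction with a practical consequence. Sections 7.4.1.2 and 8.3.3.2 disagree on what is expected, and 7.4.2.1 and 8.3.3.2 disagree on who decides. The clearest exposure is the 24-hour DSMB notice. The 7-day FDA notice and the Unanticipated Problem route are exposed to a lesser degree.

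The size is a possible delay in DSMB notice, from about 48 hours to the next scheduled review. A reader might take six months as the likely delay. It is only an upper bound: it needs 7.4.1.2 to be applied literally, no other route to reach the DSMB, meetings at the minimum frequency, and a charter that adds nothing. The charter is not among the documents and may require prompt notice of deaths. Even so, it would leave the protocol's own text contradictory. The mortality rates behind the power figures are assumptions, and the conclusion does not depend on them.

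**What to change.** Reconcile the passages in three steps.

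1. In 7.4.1.2, state that the list names events anticipated in this population, for aggregate monitoring, and does not set expectedness for suspected adverse reactions, which follows 8.3.3.2.
2. Name one party that assesses expectedness for 7.4.2.1, consistent with 8.3.3.2.
3. In 7.4.2.1, state that a death or other listed serious event assessed as at least possibly related follows the 24-hour DSMB route. This goes slightly beyond harmonizing definitions, but it closes the gap in section 7.4 for an event that is anticipated in the population and possibly related.

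Check the DSMB charter for matching wording. The cost is a protocol amendment, any matching charter edit, and a small number of extra expedited notices. No dose, treatment rule, sample size or analysis changes.
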